9.7.2.2 Sensitivity analyses

Sensitivity analyses will be performed around the start and stop of treatment to account for differences in the mode of action of rivaroxaban, vitamin K antagonists and other comparators. This will be taken into account in the analyses of outcomes. Analysis of data gathered in the drug utilization/patient characteristics part of the study will allow for the recognition of any unexpected biases, which can subsequently be accounted for in the outcomes analyses.

9.8 Quality control

For each outcome, potential cases will be identified using ICD-9-CM diagnostic codes ([Annex 3](#)) from discharge diagnosis records in the hospital database. If additional information is needed to determine the case, then PHARMO will apply for medical chart review in the hospital where the case was admitted. However, approval is needed from the database provider (Dutch National Medical Register) as well as the individual hospitals.

9.9 Limitations of the research methods

Limitations of this study include:

- The possibility for unmeasured confounders for bleeding affecting the data e.g. inadequate or missing recording of ethnicity, alcohol intake or over-the-counter use of some medications.
- Underreporting of events occurring in-hospital i.e. bleeding events occurring during admission for another diagnosis are not recorded as a primary diagnosis and recoding of secondary diagnoses are not mandatory.
- Prescriptions started in-hospital or events in the immediate post-discharge period may be missed from outpatient (pharmacy and general practitioner) records.
- Inadequate data concerning medication compliance.
- Potential for misclassification of exposure to vitamin K antagonist due to complex dosing with multiple strengths of tablet.
- For the effectiveness outcome of DVT/PE, it is possible that discharge diagnoses may lack sensitivity, and data may need to be interpreted with caution ([Severinsen et al. 2010](#)).

9.10 Other aspects

None applicable.

10 Protection of human subjects

The study will be conducted in accordance with Good Epidemiology Practices ([ISPE 2007](#)). Ethical approval will not be relevant because all data sources used are anonymous and are linked through probabilistic linkage using demographic variables of the patients. All other identifying information will be deleted after linkage of the various databases. This approach is approved by the Dutch Data Protection Authority ('College Bescherming Persoonsgegevens'). Confidentiality of patient records

will be maintained at all times. All analyses of electronic records will be performed using appropriately de-identified data without access to personal identifying information. All study reports will contain aggregate data only and will not identify individual patients or physicians. Medical record abstraction, if available, will only be performed after receiving a waiver of authorization from the relevant data holder's privacy board and approval from an Institute Review Board (IRB). At no time during the study will the sponsor receive patient identifying information except when it is required by regulations in case of reporting of adverse events.

11 Management and reporting of adverse events/adverse reactions

As per the EMA Guideline on Good Pharmacovigilance Practices (Module VI–Management and reporting of adverse reactions to medicinal products), for non-interventional study designs that are based on secondary use of data, individual reporting of adverse reactions is not required. Reports of adverse events/reactions will be summarized in the study report ([European Medicines Agency 2012](#)).

12 Plans for disseminating and communicating study results

- The study is registered on clinicaltrials.gov (NCT01947985) and will be registered on the ENCePP/EU PAS Register website once PRAC approval is achieved.
- Reports will be shared with the authorities as outlined in [Section 6](#).
- Routine updates will be provided annually in the PBRER.
- The principal investigator intends to present and/or publish data from this study in internationally recognised forums following Good Publication Practice.

13 List of references

European Medicines Agency (2012) "Guideline on good pharmacovigilance practices (GVP) Module VI – Management and reporting of adverse reactions to medicinal products."

Herings RMC, P. L. (2012). Pharmacy -based Medical Record Linkage Systems, John Wiley & Sons Ltd.

Annex 1. List of stand-alone documents

Table 3: List of stand-alone documents

None.

Annex 2. ENCePP checklist for study protocols

ENCePP Checklist for Study Protocols (Revision 2, amended)

Adopted by the ENCePP Steering Group on 14/01/2013; Doc.Ref. EMA/540136/2009

Study title:

A pharmacoepidemiological study of rivaroxaban use and potential adverse outcomes in routine clinical practice in the Netherlands.

Study reference number:

Section 1: Milestones	Yes	No	N/A	Page Number(s)
1.1 Does the protocol specify timelines for				
1.1.1 Start of data collection ¹				8
1.1.2 End of data collection ²				8
1.1.3 Study progress report(s)				8
1.1.4 Interim progress report(s)				8
1.1.5 Registration in the EU PAS register				8
1.1.6 Final report of study results.				8

Comments:

Section 2: Research question	Yes	No	N/A	Page Number(s)
2.1 Does the formulation of the research question and objectives clearly explain:				
2.1.1 Why the study is conducted? (e.g. to address an important public health concern, a risk identified in the risk management plan, an emerging safety issue)				9
2.1.2 The objective(s) of the study?				9, 10
2.1.3 The target population? (i.e. population or subgroup to whom the study results are intended to be generalised)				9
2.1.4 Which formal hypothesis (-es) is (are) to be tested?				
2.1.5 If applicable, that there is no a priori hypothesis?				

Comments:

¹ Date from which information on the first study is first recorded in the study dataset or, in the case of secondary use of data, the date from which data extraction starts.

² Date from which the analytical dataset is completely available.

Section 3: Study design	Yes	No	N/A	Page Number(s)
3.1 Is the study design described? (e.g. cohort, case-control, randomised controlled trial, new or alternative design)				10
3.2 Does the protocol specify the primary and secondary (if applicable) endpoint(s) to be investigated?				9,10
3.3 Does the protocol describe the measure(s) of effect? (e.g. relative risk, odds ratio, deaths per 1000 person-years, absolute risk, excess risk, incidence rate ratio, hazard ratio, number needed to harm (NNH) per year)				17,18

Comments:

--

Section 4: Source and study populations	Yes	No	N/A	Page Number(s)
4.1 Is the source population described?				16
4.2 Is the planned study population defined in terms of:				
4.2.1 Study time period?				12
4.2.2 Age and sex?				12
4.2.3 Country of origin?				12
4.2.4 Disease/indication?				12,13
4.2.5 Co-morbidity?				12,13
4.2.6 Seasonality?				
4.3 Does the protocol define how the study population will be sampled from the source population? (e.g. event or inclusion/exclusion criteria)				12

Comments:

--

Section 5: Exposure definition and measurement	Yes	No	N/A	Page Number(s)
5.1 Does the protocol describe how exposure is defined and measured? (e.g. operational details for defining and categorising exposure)				
5.2 Does the protocol discuss the validity of exposure measurement? (e.g. precision, accuracy, prospective ascertainment, exposure information recorded before the outcome occurred, use of validation sub-study)				
5.3 Is exposure classified according to time windows? (e.g. current user, former user, non-use)				17
5.4 Is exposure classified based on biological mechanism of action and taking into account the pharmacokinetics and pharmacodynamics of the product?				
5.5 Does the protocol specify whether a dose-dependent or duration-dependent response is measured?				

Comments:

--

Section 6: Endpoint definition and measurement	Yes	No	N/A	Page Number(s)
6.1 Does the protocol describe how the endpoints are defined and measured?				13–15
6.2 Does the protocol discuss the validity of endpoint measurement? (e.g. precision, accuracy, sensitivity, specificity, positive predictive value, prospective or retrospective ascertainment, use of validation sub-study)				18

Comments:

--

Section 7: Confounders and effect modifiers	Yes	No	N/A	Page Number(s)
7.1 Does the protocol address known confounders? (e.g. collection of data on known confounders, methods of controlling for known confounders)				12,13
7.2 Does the protocol address known effect modifiers? (e.g. collection of data on known effect modifiers, anticipated direction of effect)				

Comments:

--

Section 8: Data sources	Yes	No	N/A	Page Number(s)
8.1 Does the protocol describe the data source(s) used in the study for the ascertainment of:				
8.1.1 Exposure? (e.g. pharmacy dispensing, general practice prescribing, claims data, self-report, face-to-face interview, etc.)				16
8.1.2 Endpoints? (e.g. clinical records, laboratory markers or values, claims data, self-report, patient interview including scales and questionnaires, vital statistics, etc.)				16
8.1.3 Covariates?				16
8.2 Does the protocol describe the information available from the data source(s) on:				
8.2.1 Exposure? (e.g. date of dispensing, product quantity, dose, number of days of supply prescription, daily dosage, prescriber)				12,13
8.2.2 Endpoints? (e.g. date of occurrence, multiple event, severity measures related to event)				12,13
8.2.3 Covariates? (e.g. age, sex, clinical and product use history, co-morbidity, co-medications, life style, etc.)				12,13
8.3 Is a coding system described for:				
8.3.1 Diseases? (e.g. International Classification of Diseases (ICD)-10)				16
8.3.2 Endpoints? (e.g. Medical Dictionary for Regulatory				16

Section 8: Data sources	Yes	No	N/A	Page Number(s)
Activities (MedDRA) for adverse events				
8.3.3 Exposure? (e.g. WHO Drug Dictionary, Anatomical Therapeutic Chemical (ATC) Classification System)				
8.4 Is the linkage method between data sources described? (e.g. based on a unique identifier or other)				

Comments:

--

Section 9: Study size and power	Yes	No	N/A	Page Number(s)
9.1 Is sample size and/or statistical power calculated?				16

Comments:

--

Section 10: Analysis plan	Yes	No	N/A	Page Number(s)
10.1 Does the plan include measurement of excess risks?				
10.2 Is the choice of statistical techniques described?				17
10.3 Are descriptive analyses included?				17
10.4 Are stratified analyses included?				17
10.5 Does the plan describe methods for adjusting for confounding?				17,18
10.6 Does the plan describe methods addressing effect modification?				17,18

Comments:

--

Section 11: Data management and quality control	Yes	No	N/A	Page Number(s)
11.1 Is information provided on the management of missing data?				19
11.2 Does the protocol provide information on data storage? (e.g. software and IT environment, database maintenance and anti-fraud protection, archiving)				16,17
11.3 Are methods of quality assurance described?				18
11.4 Does the protocol describe possible quality issues related to the data source(s)?				18,19
11.5 Is there a system in place for independent review of study results?				

Comments:

--

Section 12: Limitations	Yes	No	N/A	Page Number(s)
12.1 Does the protocol discuss: 12.1.1 Selection biases? 12.1.2 Information biases? (e.g. anticipated direction and magnitude of such biases, validation sub-study, use of validation and external data, analytical methods)				19
				19
12.2 Does the protocol discuss study feasibility? (e.g. sample size, anticipated exposure, duration of follow-up in a cohort study, patient recruitment)				16
12.3 Does the protocol address other limitations?				18,19

Comments:

--

Section 13: Ethical issues	Yes	No	N/A	Page Number(s)
13.1 Have requirements of Ethics Committee/Institutional Review Board approval been described?				19
13.2 Has any outcome of an ethical review procedure been addressed?				
13.3 Have data protection requirements been described?				

Comments:

--

Section 14: Amendments and deviations	Yes	No	N/A	Page Number(s)
14.1 Does the protocol include a section to document future amendments and deviations?				7

Comments:

--

Section 15: Plans for communication of study results	Yes	No	N/A	Page Number(s)
15.1 Are plans described for communicating study results (e.g. to regulatory authorities)?				19
15.2 Are plans described for disseminating study results externally, including publication?				19

Comments:

--

Annex 3. Additional information: ICD-9-CM codes.

Table 4. ICD-9-CM codes for intracranial haemorrhage.

ICD-9-CM code	Description
430	Subarachnoid haemorrhage
431	Intracerebral haemorrhage
432	Other and unspecified intracranial haemorrhage

ICD-9-CM, International Classification of Diseases, Ninth Revision, Clinical Modification.

Table 5. ICD-9-CM codes for gastrointestinal bleeding.

ICD-9-CM code	Description
456.0	Esophageal varices with bleeding
456.20	Esophageal varices in diseases classified elsewhere, with bleeding
530.7	Gastroesophageal laceration-hemorrhage syndrome (Mallory-Weiss syndrome)
531.0	Acute gastric ulcer with haemorrhage
531.2	Acute gastric ulcer with haemorrhage and perforation
531.4	Chronic or unspecified gastric ulcer with haemorrhage
531.6	Chronic or unspecified gastric ulcer with haemorrhage and perforation
532.0	Acute duodenal ulcer with haemorrhage
532.2	Acute duodenal ulcer with haemorrhage and perforation
532.4	Chronic or unspecified duodenal ulcer with haemorrhage
532.6	Chronic or unspecified duodenal ulcer with haemorrhage and perforation
533.0	Acute peptic ulcer with haemorrhage
533.2	Acute peptic ulcer with haemorrhage and perforation
533.4	Chronic or unspecified peptic ulcer with haemorrhage
533.6	Chronic or unspecified peptic ulcer with haemorrhage and perforation
534.0	Acute gastrojejunal ulcer with haemorrhage
534.2	Acute gastrojejunal ulcer with hemorrhage and perforation
534.4	Chronic or unspecified gastrojejunal ulcer with haemorrhage
534.6	Chronic or unspecified gastrojejunal ulcer with haemorrhage and perforation
569.3	Haemorrhage of rectum and anus
578.0	Haematemesis
578.1	Blood in stool (melaena)
578.9	Haemorrhage of gastrointestinal tract, unspecified

ICD-9-CM, International Classification of Diseases, Ninth Revision, Clinical Modification.

Table 6. ICD-9-CM codes for urogenital bleeding.

ICD-9-CM code	Description
596.7	Haemorrhage into bladder wall
599.7	Haematuria
602.1	Congestion or haemorrhage of prostate
621.4	Haematometra
623.6	Vaginal hematoma (hematocolpos)
626.2	Excessive or frequent menstruation
626.3	Puberty bleeding
626.5	Ovulation bleeding
626.6	Metrorrhagia
626.7	Postcoital bleeding
626.8	Other specified abnormal uterine and vaginal bleeding
626.9	Abnormal uterine and vaginal bleeding, unspecified
627.0	Premenopausal menorrhagia
627.1	Bleeding, postmenopausal
878.4	Open wound of vulva

ICD-9-CM, International Classification of Diseases Ninth Revision, Clinical Modification.

Table 7. ICD-9-CM codes for other bleeding leading to hospitalization can be provided on request.

Table 8. ICD-9-CM codes for non-infective liver disease.

ICD-9-CM code	Description
570	Acute and subacute necrosis of liver
571.40	Chronic hepatitis, unspecified
571.41	Chronic persistent hepatitis
571.49	Chronic hepatitis, other
571.5	Cirrhosis of liver without mention of alcohol
571.6	Biliary cirrhosis
571.8	Other chronic nonalcoholic liver disease
571.9	Unspecified chronic liver disease without mention of alcohol
572.0	Abscess of liver
572.1	Portal pyemia
572.2	Hepatic coma
572.3	Portal hypertension
572.4	Hepatorenal syndrome
572.8	Other sequelae of chronic liver disease
573.0	Chronic passive congestion of liver
573.3	Hepatitis, unspecified
573.4	Hepatic infarction
573.8	Other specified disorders of liver
573.9	Unspecified disorder of liver

ICD-9-CM, International Classification of Diseases Ninth Revision, Clinical Modification.

Table 9. ICD-9-CM codes for deep vein thrombosis (DVT) and pulmonary embolism (PE)

ICD-9-CM code	Description
415.1	Pulmonary embolism and infarction
451.0	Phlebitis and thrombophlebitis of superficial leg veins
451.11	Deep vein thrombosis, femoral
451.19	Deep vein thrombosis, leg veins, spec
451.2	Thrombophlebitis, leg veins, unspec
451.81	Thrombophlebitis, iliac
451.89	Thrombophlebitis, spec
451.9	Thrombophlebitis, unspec
452.	Portal vein thrombosis
453.0	Budd-Chiari syndrome
453.1	Thrombophlebitis migrans
453.2	Thrombophlebitis of vena cava
453.3	Thrombophlebitis of renal vein
453.8	Venous embolism and thrombosis of deep vessels of lower extremity
671.30	Deep phlebothrombosis, antepartum, episode of care unspecified
671.31	Deep phlebothrombosis, antepartum, delivered, with or without mention of antepartum condition
671.32	Deep phlebothrombosis, antepartum, delivered, with mention of postpartum complication
671.33	Deep phlebothrombosis, antepartum, antepartum condition or complication
671.34	Deep phlebothrombosis, antepartum, postpartum condition or complication
671.40	Deep phlebothrombosis, postpartum, episode of care unspecified
671.41	Deep phlebothrombosis, postpartum, delivered, with or without mention of antepartum condition
671.42	Deep phlebothrombosis, postpartum, delivered, with mention of postpartum complication
671.43	Deep phlebothrombosis, postpartum, antepartum condition or complication
673.20	Obstetrical blood-clot embolism, unspecified as to episode of care or not applicable
673.21	Obstetrical blood-clot embolism, delivered, with or without mention of antepartum condition
673.22	Obstetrical blood-clot embolism, delivered, with mention of postpartum complication
673.23	Obstetrical blood-clot embolism, antepartum condition or complication
673.24	Obstetrical blood-clot embolism, postpartum condition or complication

ICD-9-CM, International Classification of Diseases Ninth Revision, Clinical Modification.

Table 10. ICD-9-CM codes for ischaemic stroke

ICD-9-CM code	Description
433.0	Occlusion and stenosis of basilar artery
433.1	Occlusion and stenosis of carotid artery
433.2	Occlusion and stenosis of vertebral artery
433.3	Occlusion and stenosis of precerebral arteries mult/bilat
433.8	Occlusion and stenosis of precerebral arteries, spec
433.9	Occlusion and stenosis of precerebral arteries, unspec
434.0	Cerebral thrombosis
434.1	Cerebral embolism
434.9	Occlusion of cerebral artery, unspec
435.0	Basilar artery syndrome
435.1	Vertebral artery syndrome
435.2	Subclavian steal syndrome
435.8	Transient ischemic attack, spec.
435.9	Transient ischemic attack, unspec.
436	Acute but ill-defined cerebrovascular disease

ICD-9-CM, International Classification of Diseases Ninth Revision, Clinical Modification.

Table 11. ICD-9-CM codes for myocardial infarction (MI)

ICD-9-CM code	Description
410.0	MI, acute, anterolateral
410.1	MI, acute, anterior, NOS
410.2	MI, acute, inferolateral
410.3	MI, acute, inferoposterior
410.4	MI, acute, other inferior wall, NOS
410.5	MI, acute, other lateral wall
410.6	MI, acute, true posterior
410.7	MI, acute, subendocardial
410.8	MI, acute, spec.
410.9	MI, acute, unspec.

ICD-9-CM, International Classification of Diseases Ninth Revision, Clinical Modification.

Table 12 ICD-9-CM codes related to renal impairment

ICD-9-CM code	Description
250.4	Diabetes with renal manifestations
249.4	Secondary diabetes mellitus with renal manifestations
403	Hypertensive chronic kidney disease
404	Hypertensive heart and chronic kidney disease
581	Nephrotic syndrome
583.81	Nephritis and nephropathy, NOS, in diseases classified elsewhere
585	Chronic kidney disease (no subcodes available)
586	Renal failure, unspecified
593.6	Postural proteinuria
791.0	Proteinuria
V42.0	Kidney transplant
V45.1	Renal dialysis status
V56	Encounter for dialysis and dialysis catheter care

ICD-9-CM, International Classification of Diseases Ninth Revision, Clinical Modification.

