- the specific site of bleeding originating in the upper or lower gastrointestinal tract or, more specifically, in the oesophagus, stomach, duodenum, jejunum, ileum, colon or rectum.
- for upper gastrointestinal bleeding, the lesion type being erosion, gastritis, duodenitis or peptic (gastric or duodenal) ulcer.
- the lesion type being NOT related to cancer.

Cases will be identified by hospital discharge diagnoses (ICD-9-CM).

Urogenital bleeding (Annex 3, Table 6)

A patient will have to be admitted to the hospital for urogenital bleeding, i.e. the specific site of bleeding originating in the urogenital tract.

Cases will be identified by hospital discharge diagnoses (ICD-9-CM).

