The PHARMO Network has been used in previous studies of anticoagulant use and bleeding risk ([Penning-van Beest et al. 2005](#); [Penning-van Beest et al. 2007](#); [Penning-van Beest et al. 2008](#); [van der Linden et al. 2009](#)).

Hospital discharge diagnoses in the Dutch National Medical Register are recorded using ICD-9-CM codes. Currently, Dutch hospitals are transitioning from ICD-9 to ICD-10 coding but the majority of hospitals still uses ICD-9. PHARMO will update the code lists to include ICD-10 codes as soon as most admissions are in ICD-10.

PHARMO can apply for chart review to extract additional information about a case in the hospital where he/she was admitted. However, approval is needed from the database provider (Dutch National Medical Register) as well as the individual hospitals.

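### The code lists for two of the three primary bleeding outcomes do not match their case definitions, and ICD-10 codes are added only once most admissions use ICD-10

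*Protocol*

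**What the plan says.** **Gastrointestinal bleeding.** Protocol section 9.3.2.1 requires, "for upper gastrointestinal bleeding, the lesion type being erosion, gastritis, duodenitis or peptic (gastric or duodenal) ulcer". It also requires "the lesion type being NOT related to cancer". Ascertainment is by code: "Cases will be identified by hospital discharge diagnoses (ICD-9-CM"). Annex 3, Table 5 gives the codes, among them "Esophageal varices with bleeding" (456.0), the matching code for varices in diseases classified elsewhere (456.20), and "Gastroesophageal laceration-hemorrhage syndrome (Mallory-Weiss syndrome"), code 530.7.

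**Urogenital bleeding.** The definition reads: "A patient will have to be admitted to the hospital for urogenital bleeding, i.e. the specific site of bleeding originating in the urogenital tract". Table 6 lists 15 codes, the last being 878.4, "Open wound of vulva".

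**Coding system.** All code lists printed in Annex 3 are ICD-9-CM. Section 9.4 states that hospitals are in transition to ICD-10, with the majority still on ICD-9, and then: "PHARMO will update the code lists to include ICD-10 codes as soon as most admissions are in ICD-10".

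**Use of the counts.** Section 6 puts crude incidences of the primary safety outcomes into interim reports in Q4 2015 and Q4 2017. The full outcomes analysis is due in the final report in Q4 2020.

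**The concern.** A programmer who follows Annex 3 and a reader who follows section 9.3.2.1 will count different events for two of the three primary outcomes. The gastrointestinal list can err in both directions. It admits lesions that the definition leaves out, and it has no named entry for three of the four lesion types that the definition lets in.

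The ICD-10 rule is a different problem with the same result, a miscounted numerator. Under the stated trigger, up to just under half of admissions could be coded in a system that the lists cannot read, while the patients concerned still contribute person-time. Section 9.7.2 adjusts for age and sex and, where possible, for co-medication, indication and previous bleeding admissions. Calendar time is not named, so capture that changes over time is not removed by the listed adjustments. Previous bleeding admissions and the hospital-coded renal categories (Table 12) rely on ICD-9 lists too, so a covariate and a subgroup variable share the gap.

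**Working it through.** **Step 1. Definitions against lists.**

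- Intracranial (Table 4: 430, 431, 432): the descriptions fit the three categories in section 9.3.2.1. No code conflict.
- Gastrointestinal (Table 5, 23 codes): 456.0, 456.20 and 530.7 are upper-tract lesions outside the four permitted types, so 3 of 23 conflict. Entries whose description names gastritis, duodenitis or erosion: 0 of 23. The unspecified entries 578.0, 578.1 and 578.9 state no lesion type, so they cannot show whether the lesion condition is met.
- Urogenital (Table 6, 15 codes): 878.4 names a wound and no bleeding, so 1 of 15 conflicts.

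These are counts of codes, not of events. The documents give no event frequencies by code.

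**Step 2. The plan's own power figure.** Inputs from section 9.5: 12,000 and 48,000 patient-years, 5 events per 1000 person-years, exclusion of a 50% increase, power 80%. Alpha is not stated there; two-sided 0.05 is assumed from the 95% intervals in section 9.7.2.

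- Expected events with a true rate ratio of 1: 12,000 × 0.005 = 60 and 48,000 × 0.005 = 240.
- SE of the log rate ratio = √(1/60 + 1/240) = 0.144.
- Power = Φ(ln 1.5 / SE − 1.96) = Φ(2.81 − 1.96) = 0.802.

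The stated 80% reproduces. It presumes that every event is captured. It concerns haemorrhagic stroke, so the Table 5 and 6 mismatches do not alter it; missed ICD-10 admissions would.

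**Step 3. Loss of a share m of events, equal in both cohorts (m assumed).** Power = Φ(2.81 × √(1 − m) − 1.96). Patient-years for 80% power = 299 / (0.005 × (1 − m)), where 299 is the number of events needed at 1:4 allocation.

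- m = 5%: 285 events, power 0.78, about 62,900 patient-years
- m = 10%: 270 events, power 0.76, about 66,400
- m = 20%: 240 events, power 0.71, about 74,800
- m = 30%: 210 events, power 0.65, about 85,400
- m = 40%: 180 events, power 0.59, about 99,700
- m = 49%: 153 events, power 0.52, about 117,300

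The 49% case is a ceiling: it holds throughout follow-up a share that the trigger allows only just before the update.

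**Step 4. Rate ratio under loss.** Observed RR = true RR × (1 − loss in rivaroxaban) / (1 − loss in comparator).

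- Equal loss: the factor is 1, no bias.
- 20% v 10%: 0.80/0.90 = 0.89. 30% v 15%: 0.70/0.85 = 0.82. 40% v 20%: 0.60/0.80 = 0.75.
- Reversed, 10% v 20%: 0.90/0.80 = 1.13.

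The documents do not say which of these applies.

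**Step 5. Off-definition gastrointestinal codes.** If a share f of comparator coded events lies outside the definition and is unrelated to the drug (both assumed), a true RR of 1.5 appears as 1.5 × (1 − f) + f. For f = 2%, 5%, 10% and 20% this gives 1.49, 1.475, 1.45 and 1.40.

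**The case against.** Several stronger readings are tempting, and the documents do not carry them.

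- *Nothing corrects the lists.* Sections 9.3.2 and 9.8 call coded cases potential cases for every outcome, and section 9.8 provides for an application for chart review where more information is needed. The safeguard exists but is weak. It depends on approval by the register and by each hospital, section 9.3.2.1 does not name it for gastrointestinal or urogenital bleeding, and reviewing coded cases cannot find bleeds that carry no listed code.
- *All primary lists are wrong.* Table 4 fits its definition.
- *The final rate ratio is biased in rivaroxaban's favour.* Section 9.4 says when the lists change, not that the changed lists will skip earlier ICD-10 admissions. Final data are due in Q4 2019 and the comparative analysis in Q4 2020, so a list run over all data would recover the events; a statistical analysis plan could say so. The documents give no uptake by year, and both cohorts enrol over the same dates, so later concentration of rivaroxaban person-time is an assumption.
- *Varices and lacerations are wrongly counted and must go.* Section 9.3.2.1 names the oesophagus as a qualifying site, and section 9.3.2 treats bleeding that leads to admission as clinically relevant. The lesion list may be the error rather than the table. Nor do the documents say that such bleeds are unrelated to anticoagulation, which Step 5 assumes.
- *Gastritis and erosion bleeds count only under unspecified codes.* That depends on coding conventions that the protocol does not show.

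What stands is the disagreement between text and tables, and a trigger that the protocol itself fixes at a point after ICD-10-coded admissions have begun.

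**Conclusion.** The point holds for two of three primary outcomes. Three of 23 gastrointestinal codes and one of 15 urogenital codes fall outside their definitions as written, and three of the four permitted upper-tract lesion types have no named code. This needs no assumption.

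The ICD-10 rule, followed as written, under-counts any interim crude incidence that is issued before the update and covers ICD-10-coded admissions. It reaches the final rate ratios only if the updated lists are not applied back, which the protocol leaves open.

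Neither the size nor the direction of the overall effect can be derived from the documents. Under an assumed equal loss of 5% to 49%, power for the stated target falls from 0.80 to 0.78–0.52 with no bias in the rate ratio. Bias arises only if loss differs between cohorts, and its sign depends on which loses more. The sample-size figure itself is correct.

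**What to change.** 1. Reconcile section 9.3.2.1 with Table 5. Either widen the lesion definition to cover varices and Mallory-Weiss syndrome, or move 456.0, 456.20 and 530.7 to a separately reported category. State which is intended.
2. Add codes for haemorrhagic gastritis, duodenitis and erosion where the register has them.
3. Remove 878.4 from Table 6, or require an accompanying bleeding diagnosis.
4. Replace the majority trigger in section 9.4 with mapped ICD-10 lists for every outcome and for the code-based covariates. Apply them according to the coding system of each admission, from the first ICD-10-coded admission, in the interim and final analyses, and show rates by coding system.

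Cost: an edit to Annex 3 and section 9.3.2.1, and an ICD-10 mapping that the protocol already promises, done sooner. Case counts will change slightly.
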